Diagnosis and main criteria for inclusion /exclusion	Key inclusion criteria: 
 • Men or women ≥ 18 years of age • T2DM as defined by the American Diabetes Association • Diagnosis of DKD with at least one of the following criteria at Run-in and Screening visits: 
 – persistent high albuminuria ¹ and presence of diabetic retinopathy OR – persistent very high albuminuria ². • Pretreated for at least 4 weeks prior to the Screening Visit with either ACEI or ARB at maximal tolerated labeled dose, preferably without adjustments to dose or choice of agent or other treatment • Serum potassium ≤ 4.8 mmol/L. Key exclusion criteria: 
 • Confirmed significant non-diabetic renal disease, including clinically relevant renal artery stenosis • Uncontrolled arterial hypertension (ie, mean sitting SBP ≥ 170 mmHg, sitting DBP ≥ 110 mmHg at run-in visit, or mean sitting SBP ≥ 160 mmHg, sitting DBP ≥ 100 mmHg at screening) • Clinical diagnosis of chronic HFrEF and persistent symptoms (NYHA class II – IV) at run-in visit (class 1A recommendation for MRAs) • Dialysis for acute renal failure within 12 weeks of run-in visit • Renal allograft in place or scheduled within next 12 months • HbA1c $> 12\%$.
Study design	Randomized, double-blind, placebo-controlled, parallel-group, multicenter, event-driven
Methodology	Randomized subjects will be treated with finerenone or placebo OD in a blinded fashion. The starting dose of study drug will depend on the subject's eGFR level at the Screening Visit: a lower dose of 10 mg OD if eGFR was

¹ **High albuminuria** (previously known as 'micro-albuminuria') is defined as 300 mg/g $>$ UACR ≥ 30 mg/g in 2 out of 3 first morning void samples.

² **Very high albuminuria** (previously known as 'macro-albuminuria') is defined as UACR ≥ 300 mg/g in 2 out of 3 first morning void samples.

	between 25 to < 60 mL/min/1.73m ² , or the higher (target) dose of 20 mg OD if eGFR was \geq 60 mL/min/1.73m ² . Study drug may be up-titrated from Visit 2 (Month1) onwards provided potassium is \leq 4.8 mmol/L and eGFR decrease is less than 30% below the value last measured. Down-titration or interruption of study drug is permitted at any time during the study for safety reasons.
Type of control	Placebo
Data Monitoring Committee	Yes

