Thus, potassium levels and renal function will be closely monitored in this study. To minimize safety risks to the patient, starting doses of study medication will be chosen according to baseline renal function, and subsequent dose up-titration will be performed on the basis of measured potassium and eGFR values. A 2-step up-titration is consistent with current clinical practice to initiate treatment with a RAS blocker at a low dose, and to up-titrate the drug only if tolerated in order to avoid adverse effects on potassium and renal parameters. Stopping rules for temporary and permanent discontinuation or dose reduction of study drug based on potassium values will minimize the risk of hyperkalemia. At any time during the study, the investigator has the option to also down-titrate the study drug, depending on serum potassium and the progression of the underlying disease.

All protocol-related procedures, including vital signs measurements, 12-lead electrocardiograms (ECGs), echocardiography and blood and urine sampling, are non-invasive or established routine assessments in the management of patients with DKD with or without CVD.

The high risk for progression of kidney disease and fatal and non-fatal CV events in the study population of Study 16244, taken together with the beneficial results of MRAs on CVD in previous clinical trials and the results of finerenone in the Phase II studies all point towards a positive risk-benefit assessment that is in favor of the participation of subjects in this study.

4. Study objectives

The **primary objective** of this study is to:

- Demonstrate whether, in addition to standard of care (SoC), finerenone is superior to placebo in delaying the progression of kidney disease, as measured by the composite endpoint of time to first occurrence of kidney failure, a sustained decrease of eGFR $\geq 40\%$ from baseline over at least 4 weeks, or renal death.

The **secondary objectives** of this study are to determine whether, in addition to SoC, finerenone compared to placebo:

- Delays the time to first occurrence of the following composite endpoint: CV death or non-fatal CV events (i.e. non-fatal myocardial infarction, non-fatal stroke, hospitalization for heart failure [HF])
- Delays the time to all-cause mortality
- Delays the time to all-cause hospitalization
- Change in UACR from baseline to Month 4

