7.4 Dosage and administration - amended

This section was changed in Amendment 3, see Section 15.1.2.8.

As shown in Table 7–2, the starting dose of finerenone will depend on the eGFR value at the Screening Visit.

Thus, at randomization, subjects with an eGFR between 25 to < 60 mL/min/1.73m² at the Screening Visit (central laboratory results) will be assigned to the lower dose of finerenone (10 mg) or placebo in addition to SoC, whilst subjects with an eGFR ≥ 60 mL/min/1.73m² will be assigned to the higher dose of finerenone (20 mg) or placebo in addition to SoC.

Table 7–2 Dosage of study drug for administration

eGFR value at the Screening Visit, based on central laboratory results:	25 to < 60 mL/min/1.73m ²		≥ 60 mL/min/1.73m ²	
Subject randomized to group: Receives	Finerenone 10 mg finerenone OD + SoC	Placebo Placebo OD + SoC	Finerenone 20 mg finerenone OD + SoC	Placebo Placebo OD + SoC
Study drug intake	One tablet of SD once daily, preferably in the morning at approximately the same time each day.			
Missed intake	
 • If >8 hours before the next scheduled dose, the subject should take one tablet of SD as soon as possible. • If ≤8 hours of the next scheduled dose, the subject should wait and take the next tablet of SD at the usual time. 			
Up-titration of dose Allowed from Visit 2 (Month 1) onwards provided that: 
 • Potassium is ≤4.8 mmol/L ^a • eGFR decrease is less than 30% below the value measured at the last scheduled visit ^a • Must be documented in eCRF 	20 mg finerenone OD, maintain SoC	Sham-titrate, maintain SoC	Not applicable	Not applicable
Down-titration of dose 
 • Only for safety reasons (for guidance, see Section 9.7.1) • Allowed any time during the study (e.g. between scheduled visits) • Must be documented in eCRF • An unscheduled safety visit is performed within an adequate timeframe proposed by the investigator 	
 • If at higher dose of SD, down-titrate to lower dose of SD, maintain SoC • If at lower dose of SD, interrupt SD, maintain SoC 			

Abbreviations: eGFR = estimated glomerular filtration rate; SD = study drug; SoC = standard of care

^a Potassium and eGFR according to local laboratory values

Intake of study drug

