Subjects will be instructed to take one tablet of study drug, preferably in the morning, at approximately the same time each day. The study drug can be taken with a glass of water, with or without food.

Missed intake of study drug

If the subject misses his/her scheduled daily intake of study drug, he/she should consider the following 2 options before continuing study drug intake:

- (1) If intake of the missed tablet is discovered >8 hours before the next scheduled dose, the subject should take the study drug as soon as possible
- (2) If the missed intake is discovered within 8 hours of the next scheduled dose, the subject should wait and take the next tablet at the usual time.

Up- and down-titration of study drug

The investigator is encouraged to up-titrate the dose of study drug at any time once the patient has been on a stable dose for 4 weeks (± 7 days) (e.g. from Visit 2 onwards for patient starting study drug on the lower dose) either at a regular visit or an Up-titration Visit. Up-titration can be performed provided:

- the potassium concentration (local laboratory value) is ≤ 4.8 mmol/L,

AND

- eGFR decrease (local laboratory value) is less than 30% below the value measured at the last regular visit.

Subjects who started with or were up-titrated to the target dose (20 mg OD) of the study drug but who do not tolerate this dose may be down-titrated at any point during the study, including between-scheduled visits if required for safety reasons. These subjects may be up-titrated again based on the rules provided above. If the subject is already at the lower dose, the study drug can be interrupted at the investigator's discretion (refer to Section 9.7.1 for guidance). If the study drug is interrupted for more than 7 days, the study drug should be re-started at the lower dose (10 mg OD).

Subsequent to an up-titration or re-start of study drug after interruption of study drug intake for more than 7 days, the investigator should perform an Up-titration Visit 4 weeks (± 7 days) after titration or restart, in order to monitor potassium levels and renal function (see Table 9-1). If a regular study visit will be scheduled to take place 4 weeks (± 7 days) after up-titration, the monitoring of potassium and renal function is assured and no Up-titration Visit has to be performed in addition. With down-titrations, the unscheduled safety visit may need a smaller time window and should be performed at the investigator's discretion.

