9.7 Other procedures and variables

9.7.1 Monitoring of potassium - *amended*

This section was changed in Amendment 3, see Section 15.1.2.31.

Hyperkalemia is a frequent event in subjects with DKD progressing to ESRD and one of the main risks identified from previous studies with MRAs including finerenone. Potassium will be monitored closely during this study, with assessments of potassium concentration scheduled at all visits (see [Table 9–1](#) for schedule).

During treatment with study drug, all assessments of potassium, including re-tests, will be performed at both local and central laboratories. Due to sample handling and extended transportation time to the central laboratory, falsely elevated serum potassium values in centrally (but not locally) analyzed samples have been observed in previous studies with finerenone. Since the value of potassium in the local sample is usually not affected by this and results from the local laboratory are available earlier, local samples will be taken not only for safety purposes but also for dose adjustments.

Re-checking of potassium values must be done at the latest within 72 hours of the investigator being aware of results that need confirmation. The investigator can perform a re-test at any time if they consider it necessary to confirm the potassium concentration of the local or the central sample.

Adjustment of dose after start of study drug intake based on blood potassium levels is provided in [Table 9–3](#).

Table 9–3 Blood potassium: guidance for dose adjustment at Visit 2 and subsequent visits

Blood potassium (mmol/L)	Action
First sample:	
≤4.8	If on lower dose of study drug, up-titrate to higher dose. If on higher dose of study drug, continue on the same dose.
4.9 to 5.5	Continue on the same dose.
>5.5	Withhold study drug and re-check potassium within 72 hours.
Second and subsequent samples:	
≤5.0	Re-start study drug at lower dose.
>5.0	Continue to withhold study drug; continue to monitor potassium and restart study drug at the lower dose only if potassium is ≤5.0

NOTE: lower dose = 10 mg once daily; higher dose = 20 mg once daily.

The following aspects have also to be taken into consideration:

- Blood potassium should be measured 4 weeks (\pm 7 days) after re-starting treatment or dose adjustment, especially after up-titration

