9.7.2.2 Local laboratory - amended

This section was changed in Amendment 3, see Section 15.1.2.32.

In addition to samples for the central laboratory, other blood **safety samples** will be taken from Visit 1 (Day 1; baseline) onwards (see Table 9–1) for analysis at the local laboratory. These samples may be obtained up to 72 hours before a scheduled visit.

The following clinical chemistry parameters must be measured for as long as subject is not prematurely discontinued from the study drug:

- Blood potassium
- Blood creatinine (eGFR will be calculated automatically in the eCRF using the CKD-EPI formula (36)).

Up-titration of the study drug will be based on local potassium and eGFR values and must be documented in the eCRF. Down-titration of the study drug will occur for safety reasons only (for guidance, see Section 9.7.1 and Table 7–2).

Potassium values should be recorded using a single decimal point (e.g. 4.5 mmol/L or mEq/L). In the event of hyperkalemia, please see Section 9.7.1 for guidance on treatment.

In women of childbearing potential, a **pregnancy test** will be performed locally, at the Screening Visit and following randomization at yearly visits as long as the subject is not permanently discontinued from the study drug (since more than 7 days). However, pregnancy tests in subjects of childbearing potential should be performed more frequently (e.g. at every visit) if this is required by national / institutional regulations. Both serological and urine tests are acceptable.

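### Table 9-3 raises the dose from 10 to 20 mg on potassium alone, leaving out the eGFR and stable-dose conditions of Section 7.4 (low severity)

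*Protocol*

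**What the plan says.** Section 9.7.1 introduces its dosing table with "Adjustment of dose after start of study drug intake based on blood potassium levels is provided in" Table 9-3. The table's title begins by naming blood potassium and continues "guidance for dose adjustment at Visit 2 and subsequent visits". For a first sample at or below 4.8 mmol/L the action is "If on lower dose of study drug, up-titrate to higher dose"; the table note defines the two doses as 10 mg and 20 mg once daily. The points listed beneath the table cover repeat potassium measurement, discrepancies between local and central results, recurrent hyperkalemia, ECG and diet. They do not mention eGFR, and nothing in Section 9.7.1 refers back to Section 7.4 or Table 7-2.

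The rest of the protocol uses two laboratory criteria:

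- Section 7.4 joins the potassium limit with an explicit AND to a second condition: "eGFR decrease (local laboratory value) is less than 30% below the value measured at the last regular visit". It also places up-titration after 4 weeks (± 7 days) on a stable dose.
- Table 7-2 lists the same potassium limit together with "eGFR decrease is less than 30% below the value measured at the last scheduled visit".
- The synopsis gives the potassium limit and "eGFR decrease is less than 30% below the value last measured".
- Section 3.3 says "subsequent dose up-titration will be performed on the basis of measured potassium and eGFR values".
- Section 9.7.2.2 says "Up-titration of the study drug will be based on local potassium and eGFR values".

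**The concern.** The row is an instruction to act, and it is the only row in Table 9-3 that increases exposure. The others keep the dose, withhold drug, or restart at 10 mg. A site working from the table alone could therefore double the dose in a subject whose eGFR has just dropped by 30% or more, which Section 7.4 does not allow.

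Section 3.3 lists eGFR-guided up-titration among the measures that reduce risk to patients, and it does not rule out worsening renal function on finerenone. The iohexol sub-study text (Section 9.7.8.1.3) anticipates a biphasic GFR course, with a possible acute effect in the first 4 months. Up-titration opens at Month 1, inside that window. What is at stake is consistent application of a dosing-safety rule.

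**Working it through.** The protocol gives no figure to reproduce, so the check sets the up-titration rules side by side.

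| Place | Potassium | eGFR | Timing |
|---|---|---|---|
| Synopsis, Methodology | ≤4.8 mmol/L | fall <30% from the last measured value | from Month 1 |
| Section 3.3 | named, no limit | named, no limit | none |
| Section 7.4, text | ≤4.8 mmol/L, local | fall <30% from last regular visit, local | 4 weeks (± 7 days) on a stable dose |
| Table 7-2 | ≤4.8 mmol/L, local | fall <30% from last scheduled visit, local | from Month 1 |
| Section 9.7.2.2 | local, no limit | local, no limit | none |
| Table 9-3, ≤4.8 row | ≤4.8 mmol/L | **none** | from Visit 2 (Month 1) |

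Table 9-3 is the only one of the six that leaves out eGFR.

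**Where the rules part on eGFR.** Section 7.4 requires a fall of less than 30%, so up-titration is excluded when

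current eGFR ≤ (1 − 0.30) × eGFR at the last regular visit.

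Take an assumed last value of 40 mL/min/1.73m², and a subject on 10 mg with an assumed potassium of 4.6 mmol/L:

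- Cut-off: 0.70 × 40 = 28.0. A fall of exactly 30% is already excluded.
- eGFR 27: (40 − 27)/40 = 32.5%. Table 9-3 says up-titrate; Section 7.4 excludes it.
- eGFR 29: (40 − 29)/40 = 27.5%. Both allow up-titration.

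**Where they part on timing.** The earliest point the stable-dose condition allows is 4 weeks − 7 days = 21 days. At Visit 2 this will usually be met. It can matter after a restart at 10 mg: a subject seen 14 days later (assumed) with potassium 4.6 mmol/L would be up-titrated under the row but not yet under Section 7.4.

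**Which text governs.** Section 5 (Treatment Period) sends the reader to Section 7.4 for dose adjustment, and Section 9.2.8 (Up-titration Visit) does the same. Section 7.4, Table 7-2 and Section 9.7.2.2 point to Section 9.7.1 only for down-titration, interruption, or raised potassium. Section 7.4 is therefore the rule, and the Table 9-3 row is the outlier.

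**The case against.** The strongest reply is that Table 9-3 never claims to be the full up-titration rule. The section is about monitoring potassium, the table's title starts with blood potassium, and the lead-in limits it to adjustment based on potassium. A reader who follows the protocol's own pointers for up-titration arrives at Section 7.4 and meets the eGFR condition. Section 9.7.2.2 repeats the requirement shortly after the table, and has local creatinine measured alongside potassium with eGFR calculated automatically in the eCRF.

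Other text limits the consequence. Section 7.4 leaves every titration to the investigator's judgement and subordinates the target dose to safety. It also has potassium and renal function checked about 4 weeks after an up-titration. Section 8.1.1 foresees reducing or stopping study drug because of creatinine or eGFR.

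Most of this stands, and it keeps the severity low. It does not make the row right. The row states an action without qualification, its title covers Visit 2 and all later visits, and the considerations listed under it omit eGFR. For a subject in the zone of disagreement, the row and Section 7.4 cannot both be followed.

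A reader might infer that the protocol has no eGFR safeguard on up-titration. The documents contradict that: the synopsis, Sections 3.3, 7.4 (text and Table 7-2) and 9.7.2.2 all contain one.

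**Conclusion.** This is a low-severity internal inconsistency in a dosing-safety rule. One table row omits two conditions that the governing section imposes: the limit on eGFR decline and the stable-dose period. The intended rule is not in doubt, so the correction involves no design choice.

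The eGFR conflict is confined to subjects on 10 mg with potassium at or below 4.8 mmol/L and an eGFR decline of 30% or more since the last regular visit. The documents give no frequency for that combination, so no patient count can be offered. The eGFR, potassium and 14-day values used above are assumed and serve only to show where the rules separate.

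A reader might also infer that the row compromises the trial's results. Nothing supports this: it does not touch alpha, power, the endpoint definitions or the planned analyses.

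**What to change.** Make the Table 9-3 row for potassium at or below 4.8 mmol/L conditional on Section 7.4, along these lines:

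> Subject on the lower dose: up-titrate only if the other Section 7.4 conditions are also met (eGFR fall of less than 30% since the last regular visit; 4 weeks ± 7 days on a stable dose). Otherwise, do not up-titrate.

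The row should not go on to say that the subject stays on the same dose. Section 7.4 only withholds permission to increase, and Section 8.1.1 allows reduction or discontinuation for creatinine or eGFR. A default to continue would be a new instruction for the subjects whose kidney function has just worsened.

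The edit is one table row, with no new data and no change to Table 7-2 or the analysis. It is still a protocol change: it would have to reach approximately 900 centers and go through ethics review where required (Section 13.3). It is best carried in an amendment made for other reasons.

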9.7.2 Laboratory assessments

9.7.2.1 Central laboratory

The name and the address for the central laboratory service provider can be found in the documentation supplied by the vendor. Only centrally analyzed blood samples will be considered for statistical analysis, unless otherwise specified. Details of the collections, shipment of samples and reporting of results by the central laboratory will be provided to the investigators in the Laboratory Manual.

Laboratory evaluations (*hematology, HbA_{1c}, clinical chemistry and urinalysis* parameters) are shown in [Table 9–4](#). Hematology, HbA_{1c} and (full) clinical chemistry are considered as ‘*Full central laboratory*’ assessments.

Laboratory evaluations will be performed according to the visit schedule (see [Table 9–1](#)).

Table 9–4 Central laboratory parameters

Parameter	Component
Hematology	White blood cell count (WBC), red blood cell count (RBC), hemoglobin, hematocrit, mean corpuscular volume (MCV), mean corpuscular hemoglobin (MCH), MCH concentration (MCHC), platelets
Glycated hemoglobin (HbA1c)	HbA1c only
Clinical chemistry (full)	Aspartate aminotransferase (AST), alanine aminotransferase (ALT), alkaline phosphatase (AP), gamma glutamyl transpeptidase (GGT), lactate dehydrogenase (LDH), creatine kinase (CK), cholesterol (high density lipoprotein [HDL], low density lipoprotein [LDL], total), triglycerides, creatinine, eGFR (CKD-EPI), blood urea nitrogen, uric acid, bilirubin, sodium, serum potassium, magnesium, total protein, albumin, high-sensitivity C-reactive protein (hs-CRP)
Clinical chemistry (limited)	Serum creatinine, eGFR (CKD-EPI), sodium, serum potassium
Urinalysis	Urine albumin-to-creatinine ratio (UACR) will be measured in the first morning void urine samples collected at the subject's home on 3 consecutive days

9.7.2.2 Local laboratory - amended

This section was changed in Amendment 3, see Section 15.1.2.32.

In addition to samples for the central laboratory, other blood **safety samples** will be taken from Visit 1 (Day 1; baseline) onwards (see Table 9–1) for analysis at the local laboratory. These samples may be obtained up to 72 hours before a scheduled visit.

The following clinical chemistry parameters must be measured for as long as subject is not prematurely discontinued from the study drug:

- Blood potassium
- Blood creatinine (eGFR will be calculated automatically in the eCRF using the CKD-EPI formula (36)).

Up-titration of the study drug will be based on local potassium and eGFR values and must be documented in the eCRF. Down-titration of the study drug will occur for safety reasons only (for guidance, see Section 9.7.1 and Table 7–2).

Potassium values should be recorded using a single decimal point (e.g. 4.5 mmol/L or mEq/L). In the event of hyperkalemia, please see Section 9.7.1 for guidance on treatment.

In women of childbearing potential, a **pregnancy test** will be performed locally, at the Screening Visit and following randomization at yearly visits as long as the subject is not permanently discontinued from the study drug (since more than 7 days). However, pregnancy tests in subjects of childbearing potential should be performed more frequently (e.g. at every visit) if this is required by national / institutional regulations. Both serological and urine tests are acceptable.

